5.8 TREATMENT COMPLIANCE

Study drugs will be dispensed to the subjects at Visits 2, 3, and 4 (one bottle containing 68 capsules at every visit).

On days of visits during the treatment period, the morning dose of study drug will be taken at the clinical site, under the supervision of the clinical staff. All other study drug intakes (evening dose and morning dose on all days without visits) will be done at home. When taking their study drug at home, subjects will be asked to record their home study drug intake in the ePRO diary. Subjects will also be asked to return all unused study drugs.

Compliance towards study drug intake will be assessed by counting returned dosage units in addition to ePRO entries upon study drug intake. Any discrepancies between returned dosage units and dosing in the ePRO diary will be discussed with the subject for whom a discrepancy was seen and recorded in the source documents and the eCRF. If a subject demonstrates continued non-compliance with study drug dosing, despite educational efforts, the Investigator should contact the Sponsor to discuss withdrawal of the subject from the study.

6. PRIOR AND CONCOMITANT THERAPY

The use of concomitant therapies should be kept at a minimum throughout the study. All therapies (prescriptions and over-the-counter medications) other than the study drug administered from informed consent until the last study visit must be recorded in the source documents and in the concomitant therapy section of the eCRF (name of the drug, dosage, route and dates of administration).

If a concomitant medication is started later than 2 weeks after the last intake of study drug, it will only be recorded when linked to a protocol-related (S)AE.

6.1 PERMITTED CONCOMITANT THERAPIES

Any medications, other than those excluded by the protocol (see Section [6.2](#)), that are considered necessary for a subject's welfare or will not interfere with the study drug, may be given at the discretion of the Investigator.

The use of analgesics is permitted on an as-needed basis. Prophylactic use is not allowed due to potential impact on the efficacy endpoints of this study.

The use of stable doses (defined as no relevant dose changes within 3 months prior to screening) of thyroid replacement therapy is allowed. The use of stable doses (defined as no relevant dose changes within 3 months prior to screening) of antihypertensive medication is allowed on the condition that hypertension is under control.

Occasional use (defined as less than 3 times per week) of benzodiazepine or Z-drugs can be allowed on an as-needed basis.

6.2 PROHIBITED CONCOMITANT THERAPIES

Prophylactic use of analgesics is not allowed due to potential impact on the efficacy endpoints of this study.

Current use of hormonal medications such as hormone therapy or hormonal contraception or any treatment for hot flashes (prescription, over-the-counter, or herbal) is not allowed during the study. These treatments must be discontinued at least 6 weeks prior to screening.

Other medications that should be washed-out prior to screening and are not allowed during the study are:

- 12 weeks wash-out:
 - ✓ tricyclic antidepressants
 - ✓ selective noradrenaline reuptake inhibitors
 - ✓ selective serotonin reuptake inhibitors (SSRIs)
 - ✓ lithium
 - ✓ oral neuroleptics
 - ✓ all sedatives
 - ✓ all hypnotics

Note that occasional use (defined as less than 3 times per week) of benzodiazepine or Z-drugs can be allowed on an as-needed basis.

- 4 weeks wash-out:
 - ✓ fluoxetine
 - ✓ monoamine oxidase inhibitors (MAOIs)

The Sponsor must be notified in advance (or as soon as possible thereafter) of any instances in which prohibited therapies are administered.

Any medication that is not explicitly covered by the permitted and non-permitted medication sections can only be allowed after discussion with the Medical Monitor.

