6. Medical condition or chronic disease (including history of neurological [including cognitive], hepatic, renal, cardiovascular, gastrointestinal, pulmonary [e.g., moderate asthma], or endocrine disease) or malignancy that could confound interpretation of the study outcome;
7. Any psychological disorder according to the criteria indicated in the Diagnostics and Statistical Manual of Mental Disorders (DSM, 4th edition) within one year prior to screening. Such disorders include but are not limited to current major depression, alcohol (more than 3 glasses of wine, beer, or equivalent/day) or substance abuse/dependence;
8. Judged by the Investigator to be unsuited to participate in the study, based on findings observed during physical examination, vital sign assessment, or 12-lead ECG;
9. History of severe allergy, hypersensitivity, or intolerance to drugs in general, including the study drug and any of its excipients;

10. Presence or sequelae of gastrointestinal, liver, kidney or other conditions known to interfere with the absorption, distribution, metabolism, or excretion (ADME) mechanisms of drugs, as judged by the Investigator;
11. Concurrent participation in another interventional study (or participation within 3 months prior to screening in this study);
12. History of poor compliance in clinical studies;
13. Unable or unwilling to complete the study procedures;
14. Subject is the Investigator or any sub-investigator, research assistant, pharmacist, study coordinator, or other staff or relative thereof, who is directly involved in the conduct of the study.

Test Product, Dose, Mode of Administration:

ESN364 capsules to be taken orally b.i.d. with a glass of tap water at room temperature. The dose level of ESN364 that will be investigated is 90 mg b.i.d. (total daily dose of 180 mg)

Reference Product, Dose, Mode of Administration:

Matching placebo capsules to be taken orally b.i.d. with a glass of tap water at room temperature.

Study/Treatment Duration:

The total duration of involvement for each subject, screening through study exit, will be at most 19 weeks: the study will consist of a screening period (screening is to be performed within 4 weeks prior to the first intake of study drug, with a minimum of 7 days to allow for baseline data collection of Hot Flash Score and Hot Flash Frequency) and a 12-week double-blind treatment period (Weeks 1-12). A follow-up visit will be scheduled 2-3 weeks after the last study drug intake.

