4.2 EXCLUSION CRITERIA

Subjects meeting any of the following criteria are excluded from participation in this study:

1. Use of a prohibited therapy or not willing to wash-out drugs as mentioned in the prohibited therapies section (Section 6.2);
2. History (in the past year) or presence of drug or alcohol abuse;
3. Suicide attempt in the past 3 years;
4. Previous or current history of a malignant tumor (except basal cell carcinoma);
5. Active liver disease or jaundice, or out-of-range values of alanine aminotransferase (ALT) and aspartate aminotransferase (AST); or total bilirubin >1.3 times the upper limit of normal (ULN); or creatinine >1.5 times the ULN; or estimated glomerular filtration rate (eGFR) using the Modification of Diet in Renal Disease (MDRD) formula <60 mL/min/1.73 m² at screening;
6. Medical condition or chronic disease (including history of neurological [including cognitive], hepatic, renal, cardiovascular, gastrointestinal, pulmonary [e.g., moderate asthma], or endocrine disease) or malignancy that could confound interpretation of the study outcome, as judged by the Investigator;
7. Any psychological disorder according to the criteria indicated in the Diagnostics and Statistical Manual of Mental Disorders (DSM, 4th edition) within one year prior to screening. Such disorders include but are not limited to current major depression, alcohol (more than 3 glasses of wine, beer, or equivalent/day) or substance abuse/dependence;
8. Judged by the Investigator to be unsuited to participate in the study, based on findings observed during physical examination, vital sign assessment, or 12-lead ECG;
9. History of severe allergy, hypersensitivity, or intolerance to drugs in general, including the study drug and any of its excipients;
10. Presence or sequelae of gastrointestinal, liver, kidney or other conditions known to interfere with the ADME mechanisms of drugs, as judged by the Investigator;
11. Concurrent participation in another interventional study (or participation within 3 months prior to screening in this study);
12. History of poor compliance in clinical studies;
13. Unable or unwilling to complete the study procedures;
14. Subject is the Investigator or any sub-investigator, research assistant, pharmacist, study coordinator, or other staff or relative thereof who is directly involved in the conduct of the study.

5. **TREATMENT(S)**

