Collection of hot flashes severity and frequency will be started on an ad hoc basis, but at a minimum twice-daily (morning and evening), via ePRO diary. Data on hot flash severity and frequency collected during the screening period will serve as baseline for Hot Flash Score and Hot Flash Frequency.

An overview of the assessments to be performed at the screening visit is provided in the [Time and Events Schedule](#).

Adverse events and concomitant therapies will be collected from signing of informed consent onwards (screening) through the follow-up visit.

All results from the screening procedure that are needed to evaluate eligibility, including the clinical laboratory results, must be available prior to randomization (Visit 2). Any abnormal assessment at the screening visit will be assessed according to its clinical relevance, and if found relevant, the subject will not be included in the study.

Unscheduled visits may be planned to assess, confirm, and follow-up on an out-of-range clinical laboratory test, vital sign, or ECG value that will determine a subject's eligibility, or in case of a positive urine drug screen. Results of this retest must be available prior to randomization. The result of the retest will be considered for subject eligibility. Findings made during unscheduled visits should be reported in the source documents and in the designated sections of the eCRF.

For screening failures, demographic data, the date of screening and signature of the ICF, and the reason(s) for screening failure will be recorded on the eCRF.

7.1.2 *Treatment Period (Visits 2-5; Weeks 1-12)*

Visit 2 should be scheduled in the morning between 7:00 and 10:00 AM, fasted. In- and exclusion criteria will be reassessed. Eligible subjects will be randomized in a 1:1 ratio to one of the 2 treatment arms (ESN364 90 mg b.i.d. or placebo). Predose assessments for efficacy (questionnaires), PK (ESN364 plasma concentrations), PD (hormone concentrations), and safety (clinical laboratory testing, bone density marker concentrations, vital signs, ECG, and physical examination) parameters will be made to serve as baseline (except for Hot Flash Score and Hot Flash Frequency, for which baseline will be data collected during the screening period).

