- deviations from or changes to the protocol to eliminate immediate hazard to the subjects;
- report of death of any subjects under the Investigator's care;
- notification if a new Investigator is responsible for the study at the clinical site;
- Development Safety Update Report, Short-Term Study Specific Safety Summary and Line Listings, where applicable;
- any other requirements of the IEC/IRB.

For all protocol amendments (excluding the ones that are purely administrative, with no consequences for subjects, data or study conduct), the amendment and applicable ICF revisions must be submitted promptly to the IEC/IRB for review and approval before implementation of the change(s), except when necessary to eliminate immediate hazard to the study subjects. If a deviation from or a change to the protocol was implemented to eliminate an immediate hazard to study subjects, then the implemented deviation or change, the reasons for it, and, if appropriate, the protocol amendment should be submitted to the IEC/IRB as soon as possible.

The Investigator (or Sponsor where required) will notify the IEC/IRB about the study completion within 90 days after the end of the study (defined as LPLV).

11.2.3 *Informed Consent*

Each subject must give written consent according to local requirements after the nature of the study has been fully explained. The consent form must be signed before performance of any study-related activity. The consent form that is used must be approved by both the Sponsor and the reviewing IEC/IRB. The informed consent should be in accordance with the principles that originated in the Declaration of Helsinki, current ICH and GCP guidelines, applicable regulatory requirements, and Sponsor policy.

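### Wash-out of prohibited drugs (4, 6 or 12 weeks) must be finished before screening, but consent and AE recording are scheduled to start only at screening

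*Protocol*

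**What the plan says.** Section 6.2 sets three wash-out lengths, all ending at screening. For hormonal medication and any treatment for hot flashes: "These treatments must be discontinued at least 6 weeks prior to screening". For the remaining drugs the lead-in is "Other medications that should be washed-out prior to screening and are not allowed during the study are", followed by two lists. The one headed "12 weeks wash-out" covers tricyclics, noradrenaline and serotonin reuptake inhibitors, lithium, oral neuroleptics, sedatives and hypnotics. The one headed "4 weeks wash-out" covers fluoxetine and MAOIs.

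Exclusion criterion 1 (section 4.2 and synopsis) reads: "Use of a prohibited therapy or not willing to wash-out drugs as mentioned in the prohibited therapies section". A woman who uses such a drug and is willing to stop it is thus not ruled out.

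The Time and Events Schedule marks informed consent at Visit 1 only, and section 7.1.1 describes it as part of that visit. The same section states: "Adverse events and concomitant therapies will be collected from signing of informed consent onwards (screening) through the follow-up visit". Section 11.2.3 sets the general rule: "The consent form must be signed before performance of any study-related activity". Inclusion criterion 8 likewise requires signature ahead of any study-related procedure.

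The synopsis gives the length of participation: "The total duration of involvement for each subject, screening through study exit, will be at most 19 weeks".

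**The concern.** Stopping an effective medicine in order to qualify for a trial is something a woman does because of the trial, and it carries some risk. Under the timetable as written, that step comes before she has signed anything and before the study records adverse events or concomitant therapies. The schedule contains no wash-out visit and no earlier consent contact.

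The candidates concerned are not remote from the target population. Section 1.1.1 describes hormone therapy as both the most effective and the most commonly used drug treatment for hot flashes, and entry requires at least 49 moderate or severe events in 7 days. A woman who stops treatment, deteriorates and then fails screening would leave little trace: for screening failures, section 7.1.1 asks only for demographic data, the dates of screening and consent signature, and the reason for failure.

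What is at stake is subject protection and consistency between the consent rule and the visit schedule, rather than the efficacy analysis.

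**Working it through.** The check is a timeline.

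**Inputs**
- Screening: at least 7 days (1 week) and at most 4 weeks before first dose (section 7.1.1).
- Treatment: 12 weeks. Follow-up: 2 to 3 weeks after the last dose (section 3.1).
- Wash-out before screening: 4, at least 6, or 12 weeks (section 6.2).
- Consent, and the start of AE and concomitant-therapy recording: Visit 1 (Time and Events Schedule, section 7.1.1).

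**The protocol's own figure.** Maximum screening + treatment + maximum follow-up = 4 + 12 + 3 = 19 weeks. This reproduces the stated maximum exactly, so the 19 weeks contain no wash-out.

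**Where a compliant wash-out falls.** Latest start before first dose = wash-out + 1 week (shortest screening) to wash-out + 4 weeks (longest screening). Involvement from the start of wash-out = 19 + wash-out.

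| Drug group | Wash-out (weeks) | Latest start before first dose (weeks) | Required wash-out after scheduled consent (weeks) | Maximum time from start of wash-out to exit (weeks) |
|---|---|---|---|---|
| Fluoxetine, MAOIs | 4 | 4 + 1 = 5 to 4 + 4 = 8 | 0 | 19 + 4 = 23 |
| Hormonal and hot flash treatments | 6 (stated as a minimum) | 6 + 1 = 7 to 6 + 4 = 10 | 0 | 19 + 6 = 25 |
| 12-week list | 12 | 12 + 1 = 13 to 12 + 4 = 16 | 0 | 19 + 12 = 31 |

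The fourth column is zero in every row because the wash-out must be over by the visit at which consent is scheduled. Even the shortest wash-out equals the longest screening period, but it cannot use that period, since it is counted back from screening and not from first dose.

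**Setting the provisions side by side.** (1) Exclusion 1 foresees wash-out for entry. (2) Section 6.2 requires it to be complete before Visit 1. (3) The schedule offers consent at Visit 1 and nowhere earlier. (4) Section 11.2.3 and inclusion 8 require consent first. If a wash-out done for the study counts as a study-related activity, a site that follows (1) to (3) to the letter breaches (4).

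**The case against.** The strongest reply is that section 11.2.3 already solves the problem. If a study-driven wash-out is a study-related activity, consent must come first. AE and concomitant-therapy recording is tied to the signature, so an earlier signature would bring recording forward with it, and nothing in the protocol forbids signing ahead of the Visit 1 assessments. This stands in part: a site that thinks it through can comply. But the general rule then calls for a step that the schedule, section 7.1.1 and the 19-week total do not contain, and section 7.1.1 equates consent with screening in a parenthesis. The reply shows which provision a careful site would follow; it does not remove the conflict.

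Other limits also stand. Exclusion 7 bars any DSM-IV psychological disorder in the year before screening, so many users of antidepressants, lithium or neuroleptics could not qualify by stopping them. Women who came off these drugs for unrelated reasons are not affected. The consent form and recruiting material are not available here, so how wash-out is explained to candidates cannot be judged.

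Three stronger readings are tempting and are not supported:
- A reader might infer that the 19 weeks is an error. It is defined from screening to exit and is exact for that span.
- A reader might infer that drug stop dates rest on recall. The text does not say so; Visit 1 includes a thorough medical history, and prior medications are to be coded and summarised (section 9.1.1).
- A reader might infer a biased hot flash baseline. The baseline comes from the screening diary, after the required wash-out, and no bias follows from the text.

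**Conclusion.** The point holds as an internal conflict over timing. On the schedule given, all of the required 4, 6 or 12 weeks of any wash-out undertaken for the study would precede both consent and AE and concomitant-therapy recording, against section 11.2.3 and inclusion 8.

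This rests on two assumptions: that some women would stop a drug in order to enter, which exclusion 1 foresees, and that doing so is a study-related activity. In practice it concerns mainly hormonal and hot flash treatments. The number of such women is not given and could be small or nil. No defect in randomisation, blinding, endpoint or analysis follows. Severity is moderate: it deserves correction because it touches consent and safety recording.

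**What to change.** Reconcile sections 4.2, 6.2, 7.1.1, 11.2.3 and the Time and Events Schedule so that the consent form is signed before any wash-out undertaken for the study, and state that AE and concomitant-therapy recording starts at that signature. The parenthesis in section 7.1.1 that equates consent with screening needs to change with it.

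The 19-week statement can stay for the span it defines. If consent moves ahead of wash-out, add the total involvement counted from consent: up to 23, 25 or 31 weeks with the current wash-out lengths (the 25 takes the 6-week minimum as the actual length).

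The wash-out lengths and the eligibility rules are for the sponsor; no change to them is proposed here.

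The cost is a protocol amendment, matching consent-form wording, and an earlier consent contact for those candidates who need a wash-out. Sample size and analysis are untouched.

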7. ASSESSMENTS

7.1 TIMING OF ASSESSMENTS

All visits need to be planned in the morning, fasted (for unbiased glucose, insulin, and C-peptide determination). Visit 2 should be planned to allow for first intake of study drugs at the clinical site between 7:00 and 10:00 AM. For each subject, all visits during the treatment period subsequent to Visit 2 should be planned at the same time of the day, in the morning, fasted. A deviation of \pm 1 day is allowed on the visits during the treatment period (Visits 3-5).

At Visits 2 and 5, DEXA will be performed. For practical reasons, the timing of DEXA may vary from the actual time of the visit, depending on the DEXA availability (DEXA appointment):

- The Visit 2 DEXA can be performed prior to Visit 2 during the screening period, as well as at Visit 2 but must be performed before randomization;
- The Visit 5 DEXA can be performed \pm 4 days from the actual time of Visit 5. It is however to be performed before the last dose of the study drug; in case the DEXA appointment related to Visit 5 is scheduled later in time than Visit 5, study drug intake must be continued until DEXA has been performed (study drug intake at home and recorded in the ePRO diary).

An overview of the timing of study drug intake and assessments is given in the [Time and Events Schedule](#).

All assessments will be done predose, except for 3 hours postdose blood sampling for PK and PD assessments at Visit 5 and administration of questionnaires, which can be done at any time during the visit.

7.1.1 *Screening Period (Visit 1)*

Subjects will be given a full explanation of the nature of the study and written informed consent (approved by the local ethics committee) will be obtained according to local requirements before any study-related assessment will be carried out.

Screening (Visit 1) will be performed within 4 weeks prior to the first intake of study drug (with a minimum of 7 days to allow for baseline data collection of Hot Flash Score and Hot Flash Frequency). The visit will consist of screening assessments for eligibility purposes (physical examination, thorough medical history, demographic data, vital signs, ECG, blood/urine samples for PD measurements, clinical laboratory tests, serology, urine drug screen, and urine pregnancy test). In addition, subjects will be trained in the use of the ePRO diary to record their hot flashes severity and frequency, to administer HFRDIS, and to register their study drug intake.

Collection of hot flashes severity and frequency will be started on an ad hoc basis, but at a minimum twice-daily (morning and evening), via ePRO diary. Data on hot flash severity and frequency collected during the screening period will serve as baseline for Hot Flash Score and Hot Flash Frequency.

An overview of the assessments to be performed at the screening visit is provided in the [Time and Events Schedule](#).

Adverse events and concomitant therapies will be collected from signing of informed consent onwards (screening) through the follow-up visit.

All results from the screening procedure that are needed to evaluate eligibility, including the clinical laboratory results, must be available prior to randomization (Visit 2). Any abnormal assessment at the screening visit will be assessed according to its clinical relevance, and if found relevant, the subject will not be included in the study.

Unscheduled visits may be planned to assess, confirm, and follow-up on an out-of-range clinical laboratory test, vital sign, or ECG value that will determine a subject's eligibility, or in case of a positive urine drug screen. Results of this retest must be available prior to randomization. The result of the retest will be considered for subject eligibility. Findings made during unscheduled visits should be reported in the source documents and in the designated sections of the eCRF.

For screening failures, demographic data, the date of screening and signature of the ICF, and the reason(s) for screening failure will be recorded on the eCRF.

7.1.2 *Treatment Period (Visits 2-5; Weeks 1-12)*

Visit 2 should be scheduled in the morning between 7:00 and 10:00 AM, fasted. In- and exclusion criteria will be reassessed. Eligible subjects will be randomized in a 1:1 ratio to one of the 2 treatment arms (ESN364 90 mg b.i.d. or placebo). Predose assessments for efficacy (questionnaires), PK (ESN364 plasma concentrations), PD (hormone concentrations), and safety (clinical laboratory testing, bone density marker concentrations, vital signs, ECG, and physical examination) parameters will be made to serve as baseline (except for Hot Flash Score and Hot Flash Frequency, for which baseline will be data collected during the screening period).

Baseline body composition will be assessed by means of DEXA. For practical reasons, the timing of DEXA may vary from the actual time of the visit, depending on the DEXA availability (DEXA appointment). Baseline DEXA can be performed prior to Visit 2 during the screening period, as well as at Visit 2 but must be performed before randomization.

Treatment will be dispensed (first of 3 bottles each containing 68 capsules) and the subjects will start taking their study drug in a q.d. regimen for 12 weeks. The first intake of study drug (Day 1; Visit 2) will be done at the clinical site (between 7:00 and 10:00 AM), under the supervision of the clinical staff. Also on other days of visits, the morning dose of study drug will be taken at the clinical site, under the supervision of the clinical staff. All other study drug intakes (evening dose and morning dose on all days without visits) will be done at home. When taking their study drug at home, subjects will be asked to record their home study drug intake in the ePRO diary. Also see Section 5.7 for dosing instructions.

After the start of treatment, the subjects will be asked to return to the clinical site every 4 weeks (Weeks 4, 8, 12; Visits 3, 4, 5) to follow-up on compliance, efficacy, PK, PD, and safety parameters. A second and third bottle of study drug will be dispensed at Visits 3 and 4, respectively.

Hot flashes severity and frequency will be assessed on an ad hoc basis, but at a minimum twice-daily (morning and evening), via ePRO at home from screening (Visit 1) to follow-

up (Visit 6). Other efficacy questionnaires will be administered at the clinical site on paper (LSEQ, SDS, and GCS) or in the ePRO diary (HFRDIS) at every visit from Visit 2 onwards. The questionnaires can be administered at any time during the visit.

Blood sampling for PK assessments (ESN364 plasma concentrations) will be taken at every visit during the treatment period, i.e., at Visits 2, 3, and 4 predose and at Visit 5, predose and 3 hours postdose.

Blood sampling for PD assessment (LH, FSH, E2, SHBG, leptin, insulin, C-peptide, and HBA1c) will also be performed at every visit (at Visits 2, 3, and 4 predose and at Visit 5, predose and 3 hours postdose; HBA1c at Visits 2 and 5 only). Additional back-up samples will be collected at every visit and stored for future, exploratory use.

Blood samples for clinical laboratory tests will be taken at every visit and should be taken in a fasted state (overnight fast for at least 10 hours) for unbiased glucose, insulin, and C-peptide determination. Physical examination and vital sign assessments will also be made at every visit. An ECG will be recorded at every visit except Visit 4. Levels of the bone density markers BALP and CTX will be assessed at Visits 2 and 5 only.

DEXA will be repeated at Visit 5, before the last dose of the study drug. For practical reasons, the timing of DEXA may vary from the actual time of the visit, depending on the DEXA availability (DEXA appointment). The Visit 5 DEXA can be performed ± 4 days from the actual time of Visit 5. It is however to be performed before the last dose of the study drug; in case the DEXA appointment related to Visit 5 is scheduled later in time than Visit 5, study drug intake must be continued until DEXA has been performed (study drug intake at home and recorded in the ePRO diary).

Adverse events and concomitant therapies will be collected from signing of informed consent onwards (screening) through the follow-up visit.

Compliance towards study drug intake and ePRO completion will be checked at every visit during the treatment period. Compliance towards study drug intake will be assessed by counting returned dosage units in addition to ePRO entries. Any discrepancies between returned dosage units and dosing in the ePRO diary will be discussed with the subject for whom a discrepancy was seen.

An overview of the assessments to be performed during the treatment period is also provided in the [Time and Events Schedule](#).

7.1.3 *Follow-up Period (Visit 6)*

Two to 3 weeks after the last intake of the study drug, subjects will be asked to come to the clinical site for a follow-up visit.

An overview of the assessments to be performed at the follow-up visit is provided in the [Time and Events Schedule](#).

7.1.4 *Unscheduled Visits*

Unscheduled visits can be planned for instance:

- to obtain additional information to ensure safety to the subject. Additional blood and urine samples may be taken at the discretion of the Investigator.

- to collect an additional blood sample for PK assessment if a subject discontinues the study drug due to an AE;
- to assess, confirm, and follow-up on an out-of-range clinical laboratory test, vital sign, or ECG value that will determine a subject's eligibility, or in case of a positive drug screen at screening. Results of this retest must be available prior to randomization. The result of the retest will be considered for subject eligibility.

Findings made during unscheduled visits should be reported in the source documents and in the designated sections of the eCRF.

